**Revision History**

VERSION	DATE	DESCRIPTION OF REVISIONS	REVISED BY
[REDACTED]	[REDACTED]	[REDACTED]	[REDACTED]
[REDACTED]	[REDACTED]	[REDACTED]	[REDACTED]
[REDACTED]	[REDACTED]	[REDACTED]	[REDACTED]

## STATISTICAL ANALYSIS PLAN

**Estradiol Vaginal Cream USP, 0.01%**

**Protocol/Study Number 71759501**

### **List of Abbreviations and Definition of Terms**

ADaM	Analysis Data Model
AE	Adverse Event
ANOVA	Analysis of variance
C	Celsius
CDISC	Clinical Data Interchange Standards Consortium
CI	Confidence Interval
CMH	Cochran-Mantel-Haenszel
CRF	Case Report Form
CRO	Contract Research Organization
dL	Deciliter
F	Fahrenheit
FDA	Food & Drug Administration
FSH	Follicle-stimulating hormone
Hg	Mercury
ICF	Informed Consent Form
ICH	International Conference on Harmonisation
LOCF	Last Observation Carried Forward
mcg	Microgram
MedDRA	Medical Dictionary for Regulatory Activities
mg	Milligram
miITT	modified Intent-to-Treat
mL	Milliliter
mm	Millimeter
OGD	Office of Generic Drugs
PAP	Papanicolaou
pH	Measure of acidity/alkalinity
PP	Per-Protocol
RS	Reference Standard
SAE	Serious Adverse Event
SAP	Statistical Analysis Plan
SAS	Statistical Analysis Software
SDTM	Study Data Tabulation Model
U.S.A	United States of America
VVA	Vulvar and Vaginal Atrophy

## STATISTICAL ANALYSIS PLAN

**Estradiol Vaginal Cream USP, 0.01%**

**Protocol/Study Number 71759501**

### **1. INTRODUCTION**

This Statistical Analysis Plan (SAP) is based on the final Clinical Study Protocol 71759501 (Rev 0) dated 07-25-2017. The SAP provides details on the planned statistical methodology for the analysis of the study data. The SAP also outlines the statistical programming specifications for the tables, listings and figures.

This SAP describes the study endpoints, derived variables, anticipated data transformations and manipulations, and other details of the analyses not provided in the study protocol. This SAP therefore outlines in detail all other aspects pertaining to the planned statistical analyses and presentations for this study.

The following documents were reviewed in preparation of this SAP:

- Final Clinical Study Protocol 71759501 (Rev 0) dated 07-25-2017
- Case Report Form Booklet Version 1.0 for Study No. 71759501

### **2. OBJECTIVES**

The objectives of this study are to:

1. Evaluate the therapeutic equivalence of a Test product, the generic Estradiol Vaginal Cream USP, 0.01% (Prasco LLC) to the Reference product, Estrace® Cream (Estradiol Vaginal Cream, USP, 0.01%) (Warner Chilcott) in the treatment of VVA.
2. Demonstrate the superiority of the active treatments (Test and Reference) over Placebo (vehicle) treatment in patients with VVA.
3. Compare the safety of Test, Reference and Placebo treatments in patients with VVA.

### **3. OVERALL STUDY DESIGN**

This randomized, double-blind, placebo-controlled, parallel-design, multiple-site study is designed to evaluate the clinical (therapeutic) effect of a Test product, a generic Estradiol Vaginal Cream USP, 0.01% (Prasco LLC) compared to the FDA Reference Standard (RS), Estrace® Cream (Estradiol Vaginal Cream, USP, 0.01%) (Warner Chilcott) in patients with VVA. Additionally, both the Test and Reference products will be tested for superiority against a Placebo.

Before any study-specific procedures are performed, all patients will read and sign the IRB-approved informed consent form (ICF).

Approximately █ eligible postmenopausal female patients, with a confirmed diagnosis of VVA will be randomized in a █ to one of the three study products as follows:

## STATISTICAL ANALYSIS PLAN

**Estradiol Vaginal Cream USP, 0.01%**

**Protocol/Study Number 71759501**

- **Test:** Estradiol Vaginal Cream, USP, 0.01% (Prasco LLC)
- **Reference:** Etrace® Cream (Estradiol Vaginal Cream, USP, 0.01%) (Warner Chilcott)
- **Placebo:** Placebo (Test vehicle cream) Vaginal Cream (Prasco LLC)

Following a 28-day screening period, at Visit 2 patients will be instructed to self-administer 2 grams of study product once daily at approximately the same time for seven consecutive days.

During the study, patients will visit the clinical center for a total of three scheduled visits:

- Visit 1/Screening (Day -28 to Day -1)
- Visit 2/Randomization (Day 1)
- Visit 3/End of Study (Day 8 or Day 9)

Final assessments will be carried out on Day 8 or Day 9.

Vaginal cytology and vaginal pH determination will be performed by the Investigator as a part of clinical evaluation at Visits 1 and 3. The primary statistical analysis of interest is the proportion of patients in the PP population that are identified as Responders at the end of the treatment period evaluated on Day 8 or Day 9. A Responder is defined as a patient with at least a 25% reduction from baseline in the sum of % basal/parabasal + % intermediate cells on vaginal cytology AND vaginal pH < 5.0 with a change from baseline vaginal pH of at least 0.5.

## STATISTICAL ANALYSIS PLAN

**Estradiol Vaginal Cream USP, 0.01%**

**Protocol/Study Number 71759501**

### Study Schematic

	Visit 1 (Day -28 to Day -1) Screening	Visit 2 (Day 1) Randomization	Visit 3 (Day 8 or Day 9) End of Study or Early Termination
Informed Consent	X		
Medical History and Demographics	X		
Review and Assessment of Concomitant Medications	X	X	X
Review and Assessment of Adverse Events	X	X	X
Vital Signs	X	X	X
Signs and Symptoms of VVA	X	X	X
Physical Exam	X		X
Vaginal Cytology and pH	X		X
PAP*Smear	X		
Serum FSH and Fasting Triglycerides	X		
Mammogram †	X		
Vaginal Ultrasound ‡	X		
Inclusion/Exclusion Criteria Review	X	X	
Collect and Review Patient Diary		X	X
Provide Patient Diary	X	X	
Dispense Study Product		X	
Collect Study Product			X

\*Patients with an intact uterus who do not have documentation of a PAP smear completed within the [REDACTED].

†Patients over the age of [REDACTED] who do not have documentation of a mammogram completed within the [REDACTED] before Screening will have a mammogram as part of the Screening evaluations.

‡Patients with an intact uterus will have a vaginal ultrasound as part of the Screening evaluations which will be reviewed before randomization.

## STATISTICAL ANALYSIS PLAN

## **Estradiol Vaginal Cream USP, 0.01%**

Protocol/Study Number 71759501

## 4. RANDOMIZATION AND BLINDING

Patients who meet the inclusion criteria and none of the exclusion criteria at Visits 1 and 2 will be assigned a randomization number. The randomization number will [REDACTED] [REDACTED]. Randomization numbers will be assigned immediately before dispensing of study product and in ascending sequential order, beginning with the lowest available number at the study site. Each patient kit and each dispensed study tube should include [REDACTED] [REDACTED] on the label.

### All randomized study product

At the end of the study, after all the clinical data have been entered and the study database has been locked, a copy of the randomization schedule will be sent to the statistician.

The Investigator, staff at the study site, study monitors, and data analysis/management personnel will be blinded to the patient assignment.

## 5. SAMPLE SIZE

For the primary endpoint analysis (proportion of patients in the PP population that are identified as Responders at the end of the treatment period evaluated on Day 8 or Day 9), sample size is estimated for therapeutic equivalence of the Test product to the Reference product and superiority of each of the active treatments groups over Placebo. [REDACTED]

## STATISTICAL ANALYSIS PLAN

Estradiol Vaginal Cream USP, 0.01%

Protocol/Study Number 71759501

[REDACTED]

[REDACTED]

[REDACTED]

[REDACTED]

[REDACTED]

[REDACTED]

[REDACTED]

[REDACTED]

## 6. ANALYSIS POPULATION

### **Per-Protocol (PP) Population**

The PP population will include all randomized patients who:

- Met the inclusion/exclusion criteria as defined in the protocol at Visit 1 and 2.
- Did not have any significant protocol deviations.
- Did not develop any concurrent vaginal infection or illness exhibiting symptoms similar to VVA, or symptoms that in the Investigator's opinion would interfere with primary and secondary endpoint assessments.
- Completed the last study visit (Visit 3) within window (Day 8 or Day 9).
- Were compliant with dosing between [REDACTED] of the required doses.

Any patient who withdraws from the study because of lack of efficacy will be included in the PP population as a Non-Responder, provided they did not have any significant protocol deviations that would affect treatment evaluation.

### **Modified Intent-to-Treat (mITT) Population**

The modified Intent-to-Treat (mITT) population will include all randomized patients who:

- Administered at least one dose of randomized study product.
- Had a post-randomization evaluation.

### **Safety Population**

The safety population will include all patients who are randomized and received study product.

## 7. STUDY ENDPOINTS

### Primary Efficacy Endpoint

The primary efficacy endpoint is the proportion of patients in each treatment group that are identified as Responders at the end of the treatment period evaluated on Day 8 or Day 9.

## STATISTICAL ANALYSIS PLAN

**Estradiol Vaginal Cream USP, 0.01%**

**Protocol/Study Number 71759501**

A “Responder” is defined as a patient with at least a 25% reduction from baseline in the sum of % basal/parabasal + % intermediate cells on vaginal cytology AND vaginal pH < 5.0 with a change from baseline vaginal pH of at least 0.5.

### Secondary Efficacy Endpoint

The secondary efficacy endpoint is the proportion of patients in each treatment group that are considered a Treatment Success at the end of the treatment period evaluated on Day 8 or Day 9.

A “Treatment Success” is defined as a score of 0 or 1 on Day 8 or Day 9 for the symptom identified at baseline as the most bothersome. This evaluation will be based on (one) patient self-assessed symptom of VVA (vaginal dryness, vaginal and/or vulvar irritation/itching, dysuria, or vaginal pain associated with sexual activity) on a scale of 0 to 3 where 0 = none and 3 = severe. Evaluation of vaginal bleeding during sexual activity will be based on a Score of 1 (presence) if it is identified by the patient as the most bothersome symptom at baseline and a score of 0 (absent) on Day 8 or Day 9.

Baseline is defined as the symptom score at Randomization Visit 2.

## **8. STATISTICAL ANALYSIS METHODS**

If not otherwise specified, statistical significance is defined as  $p < 0.05$  and is two-tailed. Data will be summarized with respect to demographic and baseline characteristics, efficacy variables and safety variables.

For categorical variables, the number and percent of each category within a parameter will be calculated for non-missing data. For continuous variables, statistics will include n, mean, standard deviation, median, minimum and maximum values.

All statistical analyses will be conducted using SAS®, [REDACTED]

[REDACTED]  
[REDACTED]  
[REDACTED]

### **8.1 Baseline Characteristics**

#### **8.1.1 Patient Disposition**

The patient disposition information will be summarized by study treatment group. The number of patients randomized, and the number of patients in each analysis population will be tabulated. In addition, completion status and primary reason for withdrawal will be summarized by study treatment group.

## STATISTICAL ANALYSIS PLAN

**Estradiol Vaginal Cream USP, 0.01%**

**Protocol/Study Number 71759501**

### **8.1.2 Demographic and Other Baseline Characteristics**

Baseline comparability of all treatment groups will be evaluated separately in the PP, mITT and Safety populations. The following baseline demographics (determined from their initial study visit) will be evaluated:

- Age (years)
- Gender (male/female)
- Ethnicity (Hispanic/non Hispanic)
- Race (White, Black/African American, Native Hawaiian or Other Pacific Islander, Asian, American Indian or Alaska Native, Other)
- Natural or surgical menopause
- Duration of postmenopausal status
- Baseline signs and symptoms
- Baseline % of the three major vaginal wall cell types (basal/parabasal cells, intermediate cells and superficial cells)
- Vaginal pH

Summary tables by treatment group will be presented. Continuous variables will be summarized using descriptive statistics (n, mean, standard deviation, median, minimum, maximum). Categorical variables will be summarized using frequencies and percentages.

Baseline treatment comparisons will be presented using Chi-Square test for the categorical variables, and Analysis of Variance (ANOVA) for the continuous variables.

All data will be listed by treatment and patient.

### **8.1.3 Medical History**

At Visit 1, patients will be questioned about medical history, including acute and chronic medical history and medical history relevant to their VVA.

Medical history data will be listed by treatment and patient.

### **8.1.4 Concomitant Medications**

At Visit 1, patients will be questioned about all concomitant medication use within the previous 6 months. At Visits 2 and 3, patients will be questioned about ongoing or any new concomitant medication use.

## STATISTICAL ANALYSIS PLAN

**Estradiol Vaginal Cream USP, 0.01%**

**Protocol/Study Number 71759501**

All prior and concomitant medications taken since screening until the end of the study will be listed by treatment and patient.

### **8.1.5 Physical Exam**

At Visit 1, the Investigator will perform a general physical exam including pelvic exam and breast exam. At Visit 3, the Investigator will perform a general physical exam including pelvic and breast exam. Any clinically significant abnormal findings on this exam should be reported as adverse events (AEs).

Physical examination results will be listed by treatment and patient.

### **8.1.6 Laboratory Evaluations**

At Visit 1, all patients will have a blood sample taken for evaluation of serum FSH levels. Serum FSH will be evaluated by a central clinical laboratory. [REDACTED]

All patients will have a blood sample taken for fasting triglyceride testing. These samples will be sent to the central laboratory for testing. [REDACTED]

Laboratory evaluation results will be listed by treatment and patient.

### **8.1.7 Dosing Compliance**

Patients will be considered compliant if they take a total of at least six doses and no more than eight doses, and not more than two doses on any day. Patients taking fewer than 75% or more than 125% of the required doses will be considered non-compliant with dosing. Compliance with dosing will be verified by the use of the patient diaries. Compliance criteria are as outlined in the table below:

For patients who have completed the study:

Study Design			Compliance Criteria	
Visit 3	Treatment Duration	Required Doses	Not more than 125% (doses)	Not less than 75% (doses)
Days 8-9	7 days	7	8	6

For patients who are early terminated, compliance will be determined from their duration in the study, up to the time they are considered early terminated. For example, if a patient is dropped after six days of participation and starts application of study product on the day of Visit 2 (i.e., Day 1) and once daily for the four of the five remaining days, then percent compliance would be 83% (4 out of 5 doses).

## STATISTICAL ANALYSIS PLAN

**Estradiol Vaginal Cream USP, 0.01%**

**Protocol/Study Number 71759501**

Drug administration and dosing compliance will be listed by treatment and patient.

### **8.2 Efficacy Analyses**

#### **8.2.1 Analysis of Primary Efficacy Endpoint**

##### **Therapeutic Bioequivalence Analysis**

Therapeutic equivalence of the Test product to the Reference product based on the primary endpoint will be evaluated in the PP population after the end of treatment on Day  $8 \pm 1$ .

Based on the usual method used in OGD for binary outcomes, the 90% confidence interval for the difference in success proportions between test and reference treatment should be contained within  $[-0.20, +0.20]$  in order to establish equivalence.

The compound hypothesis to be tested is:

versus

where  $\hat{p}_1$  = cure rate of test treatment  
 $\hat{p}_2$  = cure rate of reference treatment.

Let

$n_1$  = sample size of test treatment group  
 $a_1$  = number of cured patients in test treatment group  
 $n_2$  = sample size of reference treatment group  
 $a_2$  = number of cured patients in reference treatment group

, and

The 90% confidence interval for the difference in proportions between test and reference will be calculated as follows, using Yates' correction:

## STATISTICAL ANALYSIS PLAN

**Estradiol Vaginal Cream USP, 0.01%**

**Protocol/Study Number 71759501**

If the 90% confidence interval (calculated using Yates' continuity correction) for the absolute difference between the proportion of patients considered as "Responders" (at least a 25% reduction from baseline in the sum of % basal/parabasal + % intermediate cells on vaginal cytology AND vaginal pH < 5.0 with a change from baseline vaginal pH of at least 0.5) in the Test and Reference groups is contained within the range [-20%, +20%] then bioequivalence of the Test product to the Reference product will be considered to have been demonstrated for the primary endpoint.

To declare therapeutic equivalence of the Test product to the Reference product, equivalence must be demonstrated for only the primary endpoints in the PP population.

### **Superiority to Placebo Analysis**

The mITT population and LOCF will be used to evaluate the superiority of both the Test and Reference product to Placebo. LOCF will apply to each parameter of the endpoint.

Summary table with frequency and percentage on the proportion of responders by treatment group will be presented. If the proportion of Responders in the Test and the Reference product groups is numerically and statistically superior to that of the Placebo ( $p < 0.05$ ; using a two-sided CMH test, stratified by clinical site) then superiority of the Test and Reference products over Placebo will be concluded.

To declare superiority of the Test and Reference products over Placebo, their superiority must be demonstrated for only the primary endpoint in the mITT population.

### **8.2.2 Analysis of Secondary Efficacy Endpoint**

#### **Therapeutic Bioequivalence Analysis**

Similar to the analysis for primary endpoint above, therapeutic equivalence of the Test product to the Reference product based on the secondary endpoint will be evaluated in the PP population after the end of treatment on Day 8  $\pm$  1.

Secondary analysis will compare the proportion of patients considered to be a "Treatment Success" for their most bothersome symptom. A "Treatment Success" is defined as a score of 0 or 1 at Day 8 for the symptom identified at baseline as the most bothersome. Baseline is defined as the symptom score at Randomization Visit 2. If the 90% confidence interval (calculated using Yates' continuity correction) for the absolute difference between the proportion of patients considered as "Treatment Success" in the Test and Reference groups is contained within the range [-20%, +20%] then bioequivalence of the Test product to the Reference product will be considered to have been demonstrated for the secondary endpoint.

To declare therapeutic equivalence of the Test product to the Reference product, bioequivalence must be demonstrated for only the primary endpoint. Bioequivalence testing of the secondary

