10.6.6 Signs and Symptoms

At each visit, the blinded clinical staff or Investigator will question the patient regarding the severity of their symptoms. See Appendix B for rating scales. The following symptoms will be evaluated:

- Vaginal Dryness
- Vaginal/Vulvar irritation/itching
- Dysuria
- Vaginal Pain associated with Sexual Activity
- Vaginal Bleeding

The severity of each symptom will be recorded on the source documents. The patients will be asked to identify which symptom is considered to be the most bothersome symptom at each visit.

CONFIDENTIAL PROTOCOL

A Randomized, Double-Blind, Placebo-Controlled, Parallel-Design, Multiple-Site Study to Evaluate the Therapeutic Equivalence of Estradiol Vaginal Cream, USP, 0.01% (Prasco LLC) to Estrace[®] Cream (Estradiol Vaginal Cream, USP, 0.01%) (Warner Chilcott) in the Treatment of Vulvar and Vaginal Atrophy, 71759501

At Visits 1 and 2, the most bothersome symptom must have a score of moderate or severe (for vaginal dryness, vaginal/vulvar irritation/itching, dysuria, or vaginal pain associated with sexual activity) or present (for vaginal bleeding) to be eligible for inclusion in the study.

The worsening in severity of the Signs and Symptoms need not be additionally included as AEs unless the patient requires additional treatment or in the opinion of the Investigator

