11.5 Efficacy Endpoints

Primary Efficacy Endpoint

The primary efficacy endpoint is the proportion of patients in each treatment group that are identified as Responders at the end of the treatment period evaluated on Day 8 or Day 9.

A “Responder” is defined as a patient with at least a 25% reduction from baseline in the sum of % basal/parabasal + % intermediate cells on vaginal cytology AND vaginal pH < 5.0 with a change from baseline vaginal pH of at least 0.5.

Secondary Efficacy Endpoint

The secondary efficacy endpoint is the proportion of patients in each treatment group that are considered a Treatment Success at the end of the treatment period evaluated on Day 8 or Day 9.

CONFIDENTIAL PROTOCOL

A Randomized, Double-Blind, Placebo-Controlled, Parallel-Design, Multiple-Site Study to Evaluate the Therapeutic Equivalence of Estradiol Vaginal Cream, USP, 0.01% (Prasco LLC) to Estrace[®] Cream (Estradiol Vaginal Cream, USP, 0.01%) (Warner Chilcott) in the Treatment of Vulvar and Vaginal Atrophy, 71759501

A “Treatment Success” is defined as a score of 0 or 1 on Day 8 or Day 9 for the symptom identified at baseline as the most bothersome. This evaluation will be based on (one) patient self-assessed symptom of VVA (vaginal dryness, vaginal and/or vulvar irritation/itching, dysuria, or vaginal pain associated with sexual activity) on a scale of 0 to 3 where 0 = none and 3 = severe. Evaluation of vaginal bleeding during sexual activity will be based on a Score of 1 (presence) if it is identified by the patient as the most bothersome symptom at baseline and a score of 0 (absent) on Day 8 or Day 9. Refer to Appendix B for rating scales.

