### **Superiority to Placebo Analysis**

The mITT population and LOCF will be used to evaluate the superiority of both the Test and Reference products to Placebo.

Summary table with frequency and percentage on the proportion of responders by treatment group will be presented. If the proportion of Responders in the Test and the Reference product groups is numerically and statistically superior to that of the Placebo ( $p < 0.05$ ; using a two-sided CMH test, stratified by clinical site) then superiority of the Test and Reference products over Placebo will be concluded.

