## STATISTICAL ANALYSIS PLAN

**Estradiol Vaginal Cream, USP, 0.01%**

**Protocol / Study No. 71759501**

Vaginal Pain during Sexual Activity		
Suffers discomfort or pain during sexual activity that may be restrictive.		
Score	Severity	Description
0	None	No discomfort or pain
1	Mild	Some feeling of vaginal soreness or pain, during or after sexual activity. Does restrict frequency of or type of sexual activity.
2	Moderate	Vaginal pain during sexual activity such that frequency and type of sexual activity have been disrupted. Lubrication may be needed for penetration
3	Severe	Vaginal penetration very painful and impossible without vaginal lubrication. Discomfort such that frequency of sexual activity significantly reduced.

Vaginal bleeding during or after sexual activity		
Score	Severity	Description
0	Absent	No vaginal bleeding observed
1	Present	Bleeding observed during or soon after vaginal activity

At each visit each patient must also clearly identify which is the most bothersome sign/symptom to her, even if she rates two or more symptoms the same severity rating.

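### SAP 8.2.2 drops the bleeding rule from Treatment Success and, in its placebo paragraph, tests the primary endpoint instead of the secondary one

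*SAP*

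**What the plan says.** **Definition of Treatment Success.** SAP 7 and Protocol 11.5 agree. For the four graded symptoms (dryness, irritation/itching, dysuria, pain with sexual activity), scored 0 to 3, success is a score of 0 or 1. Bleeding has its own rule: present at baseline and, in the words of SAP 7, "a score of 0 (absent) on Day 8 or Day 9".

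SAP 8.2.2 restates the definition for the equivalence analysis. There, Treatment Success "is defined as a score of 0 or 1 at Day 8 for the symptom identified at baseline as the most bothersome". Nothing is said about bleeding, and there is no reference back to SAP 7.

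**Bleeding scale.** SAP Appendix A gives two levels only: 0 for absent and 1 for present, the latter described as "Bleeding observed during or soon after vaginal activity". Protocol 10.6.6 lets bleeding be the qualifying symptom: at Visits 1 and 2 the most bothersome symptom must be moderate or severe, "or present (for vaginal bleeding) to be eligible for inclusion in the study".

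**Placebo comparison.** Under the secondary-endpoint heading, SAP 8.2.2 gives this decision rule: "If the proportion of Responders in the Test and the Reference product groups is numerically and statistically superior to that of the Placebo". The table that goes with it is described thus: "Summary table with frequency and percentage on the proportion of responders by treatment group will be presented". SAP 7 defines a Responder by vaginal cytology and pH, which is the primary endpoint. Protocol 11.6 requires the superiority approach to be applied to the secondary endpoint in the mITT population.

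**Timing.** SAP 8.2.1 and 8.2.2 speak of Day 8 ± 1, and 8.2.2 also of Day 8 alone. SAP 6 and SAP 7 use Day 8 or Day 9.

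**The concern.** SAP 8.2.2 is where a programmer would look for the secondary analysis. Followed literally, it does two things the protocol does not intend.

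- A woman whose most bothersome symptom is bleeding and who still bleeds at the end of treatment is counted as a success. This pushes success rates up in every arm and, if bleeding patients respond like the others, pulls between-arm differences towards zero. For an equivalence comparison that is the direction that favours the conclusion; for the placebo comparison it costs power.
- The secondary placebo test repeats the primary test, and the two comparisons of Treatment Success with placebo (Test and Reference) are not specified at all.

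What is at stake is the secondary endpoint only.

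**Working it through.** **1. The two success rules side by side.** For a woman with bleeding as most bothersome symptom, who must have had score 1 at entry:

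| Score at Visit 3 | SAP 7 and Protocol 11.5 | SAP 8.2.2 as written |
|---|---|---|
| 0 (absent) | success | success |
| 1 (present, unchanged) | failure | success |

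The scale has no other level, so under 8.2.2 no recorded bleeding score can be a failure.

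Missing scores may add to this (an inference). The study schematic has symptoms scored at Visits 1, 2 and 3, so Visit 3 is the only score after treatment. If it is missing and LOCF carries the Visit 2 score forward, a graded symptom carries 2 or 3 and fails, while bleeding carries 1 and, under the 8.2.2 wording, succeeds.

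**2. The placebo paragraphs side by side.** The table sentence and the decision sentence in 8.2.2 match those in 8.2.1. The equivalence paragraph of 8.2.2 was rewritten for Treatment Success; the placebo paragraph was not. This needs no arithmetic: both required comparisons are named on the wrong endpoint.

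**3. Size of the bleeding error.** The plan gives no figure to reproduce.

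Inputs from the documents: about 535 patients (protocol title page) and 2:2:1 allocation (synopsis), so 535 × 2/5 = 214 per active arm and 535 × 1/5 = 107 on placebo.

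Assumptions: 80% of each active arm in the PP population (0.80 × 214 ≈ 171); a share f of women with bleeding as most bothersome symptom, equal across arms, shown from 1% to 10%; an arm success rate s of 40% to 60%.

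Let p be the correct success rate and s_b the correct success rate among bleeding patients. The 8.2.2 wording turns the failures among them into successes:

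- p′ = p + f(1 − s_b)
- p′_T − p′_R = (p_T − p_R) + f(s_bR − s_bT)

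If bleeding patients respond like the rest of their arm (s_b = s), the rise is f(1 − s) and the difference becomes (1 − f)(p_T − p_R):

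| f | Women per active arm (f × 171) | Rise in success rate, s = 60% to 40% | A 10-point difference becomes |
|---|---|---|---|
| 1% | 1.7 | 0.4 to 0.6 points | 9.9 |
| 2% | 3.4 | 0.8 to 1.2 points | 9.8 |
| 5% | 8.6 | 2.0 to 3.0 points | 9.5 |
| 10% | 17.1 | 4.0 to 6.0 points | 9.0 |

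Without that assumption the shift f(s_bR − s_bT) lies between −f and +f, so it is at most 1, 2, 5 or 10 points in either direction.

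**4. Placebo comparison, if Treatment Success is tested with the 8.2.2 definition.** Assume true success of 60% on active and 40% on placebo, also among bleeding patients, with 214 against 107, two-sided 0.05. This is an unstratified normal approximation to the CMH test: power = Φ[(Δ − 1.96·SE₀)/SE₁], with SE₀ pooled and SE₁ unpooled.

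- Correct rule: Δ = 20.0 points, SE₀ = 0.0591, SE₁ = 0.0580, power 92.7%.
- f = 1%: Δ = 19.8 points, power 92.2%.
- f = 5%: rates 62% and 43%, Δ = 19.0 points, power 90.0%.
- f = 10%: rates 64% and 46%, Δ = 18.0 points, power 86.9%.

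**The case against.** The best defence is that 8.2.2 abbreviates rather than contradicts. SAP 7 is the definitions section and holds the full bleeding rule; the sentence in 8.2.2 repeats its opening sentence apart from the day, and uses the same defined term. The word Responders can be read as a label slip: the heading says secondary endpoint, Protocol 11.6 says what is to be done, and these documents use outcome labels loosely elsewhere (SAP 8.2.1 calls the primary outcome a cure rate). Nothing in the documents supports a bleeding share of 5% to 10%; the symptom can be observed only in sexually active women, and undiagnosed vaginal bleeding is an exclusion. No decision depends on the endpoint. The table shells, which might be right, are redacted.

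Most of this stands as a limit on the consequences. The intent of the placebo paragraph is fairly clear, the size of the bleeding error rests on assumption, and what will be programmed cannot be seen. It does not make the text correct. The sentence in 8.2.2 reads as a complete definition and gives no sign that a rule is missing; no passage says which section prevails; and the placebo paragraph never mentions Treatment Success. For a bleeding score of 1, the two SAP sections classify the same patient in opposite ways.

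**Conclusion.** The concern holds. The secondary-analysis text is wrong as written on two points: the success definition cannot record a failure for bleeding, and the placebo test names the primary endpoint. The second point is certain from the text. The effect of the first is negligible if 1% to 2% of women have bleeding as most bothersome symptom and respond like the others. At 10% it takes one tenth off each between-arm difference and, in the illustration, about 6 points off power (92.7% to 86.9%). The bleeding share, the success rates and the 80% PP share are assumptions.

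The primary conclusions are not affected. Equivalence is declared on the primary endpoint alone, and for superiority SAP 8.2.1 says of the active products that "their superiority must be demonstrated for only the primary endpoint in the mITT population". SAP 8.2.2 itself calls the secondary equivalence test supportive. The timing mismatch is minor: Day 8 ± 1 would admit Day 7, but the PP definition already restricts Visit 3 to Day 8 or Day 9. The point should be corrected, but it does not threaten the trial.

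**What to change.** Amend the SAP before database lock:

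1. In the equivalence paragraph of 8.2.2, replace the restated definition with a reference to SAP 7, so that success is a score of 0 or 1 for the four graded symptoms and a score of 0 for bleeding.
2. In the placebo paragraph of 8.2.2, replace Responders, in both the table sentence and the decision sentence, with patients classed as Treatment Success, in the mITT population as Protocol 11.6 requires.
3. In 8.2.1 and 8.2.2, align the visit timing to the Day 8 or Day 9 window used in SAP 6 and SAP 7.
4. Check that the secondary-endpoint table shells follow the corrected text.

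The cost is a wording revision. Data collection, sample size and the primary decision rule do not change.
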